Since so many biologic functions depend upon correct protein and lipid glycosylation, clinical CDG manifestations are widely variable within and among subtypes and across the lifespan. The clinical findings in affected individuals reflect glycosylation's role in the embryology and biology of many organ systems. Clinical findings may include developmental delay/intellectual disability with abnormalities in brain MRI, hypotonia, failure to thrive or growth impairment, hepatopathy, coagulopathy, immunodeficiency, protein losing enteropathy, osteopenia, skeletal dysplasias, renal abnormalities, functional and/or anatomic eye involvement, endocrinopathies, and peripheral neuropathy. Some CDG present with only tissue-specific symptoms such as SEC23B-dyserythropoietic anemia or Leukocyte Adhesion Deficiency Type II.⁶

Of the known 137 glycan-synthesis disorders we have potential therapies for only 8 disorders and not all current therapies are fully effective. Clinical trials have not validated these treatments for safety and efficacy. MPI-CDG has been treated with oral mannose.⁷ In SLC35C1-CDG, some patients respond to oral fucose supplementation. This treatment is only effective for the typical recurrent infections with hyperleukocytosis and does not correct the neurological issues of these patients.⁶ PIGM-CDG, the mutation described in the only published case so far, causes histone hypoacetylation at the PIGM promoter. Butyrate controls the seizures.⁸ PGM1, a critical enzyme for the

conversion of glucose-1-phosphate to glucose-6-phosphate, is at the crossroads of the glycogen, glucose and galactose pathway. **PGM1 deficiency is treatable with D-galactose**, alleviating the hypoglycemia, coagulopathy, and endocrinopathy seen in this disorder,^{9,10} although not the cardiomyopathy. The glycosylation defect CAD-CDG has been treated with uridine.^{11,12} Magnesium can improve MAGT1-CDG. Manganese and D-galactose have been used to treat TMEM165-CDG, whereas **SLC35A2-CDG has been treated with D-galactose**. From the group of disorders of de-glycosylation preclinical trials suggested positive effect of **GlcNAc treatment in NGLY1** deficiency.

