A list of retrospective data to be collected from the medical record is attached to the application. Optional blood, stool, and urine samples will be collected for research at each annual visit (once per year over the course of 5 years of follow up). If a participant is unable to provide urine, stool, or blood samples due to age or other logistical difficulty, we will forego research sample collection and rely purely on clinical/research data collected over the course of the study. If any clinical residual samples (urine, blood, or stool) are available for these participants unable to provide fresh research collections, we may use these instead. These clinical residuals would come from the Biochemical Genetics Lab (BGL) at Mayo or from participating sites' laboratories, if any sample remains. Skin biopsies will be only taken for diagnostic purposes. Leftover tissue material from clinical diagnostics will be used for biomarker discovery. If a subject doesn't complete regular follow up appointments, we will reach out to them via phone or email to obtain follow up information and complete questionnaires to ensure we are able to obtain accurate follow up information. Participants will be offered up to \$700 reimbursement to cover lodging and travel expenses, per visit at all sites except for the University of Minnesota Masonic Children's Hospital. University of Minnesota will offer \$75 per visit to each participant as remuneration and will not offer travel reimbursement.

Accrual:

Our goal is to enroll 150 patients of all ages and from all CDG types over 5 years in the natural history study. At least 50 of the 150 enrolled subjects will have a diagnosis of PMM2-CDG. There will be no exclusion based on sex, ethnicity or socio-economic status. The sample size of 100 was based on a count of the number of affected individuals currently clinically followed and current patient census taken by CDG CARE in August of 2018.

Participating Sites:

We will collaborate with other sites on this study with Mayo Clinic acting as the IRB of record. The target accrual in total will remain at 150 participants. The sites below will be included in the study:

1. Children's Hospital of Pittsburgh at University of Pittsburgh Medical Center – PI is [name]
2. Seattle Children's Hospital – PI is [name]
3. Tulane University Medical School – PI is [name]
4. Baylor College of Medicine – PI is [name]
5. University of Minnesota Masonic Children's Hospital – PI is [name]

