Inclusion Criteria: All individuals with a genetically, enzymatically, or molecularly confirmed diagnosis of CDG or NGLY1 deficiency, or individuals whose laboratory values are highly suggestive of CDG, but who do not have a verifiable diagnosis possibly due to difficulty with clinical molecular testing will be invited to enroll. Or those without confirmatory testing, they will be enrolled as "CDG highly likely/diagnosis pending" if the site PI and study PI concur. These individuals should have their diagnosis confirmed within one year of enrollment. If not confirmed they will be removed from the study. The study requires a minimum number of 50 patients with the diagnosis PMM2-CDG.

Exclusion Criteria: none

Biospecimens

Collection of blood samples.

- a. **From healthy, non-pregnant, adult subjects who weigh at least 110 pounds.** For a minimal risk application, the amount of blood drawn from these subjects may not exceed 550ml in an 8 week period and collection may not occur more frequently than 2 times per week.
Volume per blood draw: 30ml
Frequency of blood draw (e.g. single draw, time(s) per week, per year, etc.) annually (up to 5 visits)
- b. **From other adults and children considering age, weight, and health of subject.** For a minimal risk application, the amount of blood drawn from these subjects may not exceed the lesser of 50 ml or 3 ml per kg in an 8 week period, and collection may not occur more frequently than 2 times per week.
Volume per blood draw: up to 30 ml max, will draw minimum amounts not to exceed 3 mls/kg of weight. This will be calculated for each pediatric patient
Frequency of blood draw (e.g. single draw, time(s) per week, per year, etc.) annually (up to 5 visits)

Prospective collection of biological specimens other than blood: random urine, random stool at each annual visit (once per year over 5 year follow up)

Review of medical records, images, specimens

Check all that apply (data includes medical records, images, specimens).

Only data that exists before the IRB submission date will be collected.

Date Range for Specimens and/or Review of Medical Records:

Examples: 01/01/1999 through 12/31/2015, or all records through mm/dd/yyyy.

Note: The Date Range must include the period for collection of baseline data, as well as follow up data, if applicable.

The study involves data that exist at the time of IRB submission **and** data that will be generated after IRB submission. Include this activity in the Methods section.

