With the data collected over time, the average trend with age will be estimated using mixed effects models to account for the correlation of repeated measures from a subject. The model will include fixed and random effects for the intercept and slope (age). Maximum likelihood estimates (MLE) will be obtained for regression coefficients for fixed effects and restricted MLE for the variance component. The association of a factor of interest with a response variable will be examined using mixed effects models to account for the subject specific change. For a time constant factor, the model will include the factor, age and an interaction term between the factor and age as fixed effects. The model will also include random effects for the intercept and slope (time). For a time varying factor, the model may include baseline value of the factor and the change at the next visit as fixed effects to estimate cross-sectional and longitudinal effects simultaneously.

We will compare results of PROs to NPCRS subdomain scores, physical exam findings, and laboratory findings that should be reflected in that tool to assess the validity of each PRO measure. Partial least squares (PLS) regression analysis will be utilized to identify patterns of association between the PROs and the clinical scores. The PLS analysis and significant weights may reveal novel composite scores for CDG patients. Changes in PRO scores over time will be tested for association with Quality of Life questions using random effects generalized linear regression models incorporating a random intercept for each participant. We will also compare subsequent scores on the PROs from the same subject to determine reliability of the PRO if there has been no significant interval change in the clinical status. Reliability will be assessed by the weighted Kappa to account for the ordinal variables.

Expected Outcomes.

References:

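### The test of PRO change against Quality of Life names a random intercept but no random slope, robust variance or response variable, so its standard errors can be wrong, in a direction that depends on the reading

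*Combined protocol and SAP*

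**What the plan says.** The sentence is in the PRO validation paragraph of the Data Analysis Plan, which serves Aim 2. It says that changes in PRO scores will be "tested for association with Quality of Life questions using random effects generalized linear regression models incorporating a random intercept for each participant", so the dependence structure is a random intercept per participant. For this test it names no random slope, residual correlation structure, robust variance or sensitivity model. It also leaves open which variable is the response, and whether change enters as a time trend, a visit-to-visit difference or a difference from baseline.

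The paragraph before it treats dependence differently. The age-trend model has a random intercept and a random slope for age. Associations of a factor with a response use "mixed effects models to account for the subject specific change", and for a time-constant factor, "The model will also include random effects for the intercept and slope (time"). For a time-varying factor, only fixed effects are described.

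**The concern.** The plan's one longitudinal test of PRO against Quality of Life is about change over time, yet it leaves out the term that the plan uses elsewhere for patient-specific change. If the response is the PRO score at each visit and patients progress at different rates, a random intercept leaves those trends in the residual. The model-based standard error of a Quality of Life by time term is then too small, and an unrelated question is called associated too often. If the response is a visit-to-visit difference, a random intercept is again the wrong dependence model, for another reason. At stake is the evidence that a PRO tracks quality of life: too liberal a test could support a poor measure, and too conservative a test could miss a good one.

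**Working it through.** **Inputs.** The target is 150 participants (Accrual; Subject Information). PROs are collected at every visit (Study Activities). Visits are annual, and five per participant is taken from the blood-draw schedule (Biospecimens). The plan gives no significance level, SD or effect for this test, so there is no figure of its own to reproduce. Assumed here: two-sided 5%, intercept SD 1, residual SD 0.5 or 1, slope SD 0 to 0.3 per year, a continuous score, time in years since enrolment, and Quality of Life simulated like the PRO but independent of it.

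**Reading (a): PRO score at each visit, baseline Quality of Life by time.** Let s2 be the residual variance, t2 the slope variance, T the number of visits and S the sum of squared centred visit times (10 for T = 5, 2 for T = 3). A participant's fitted slope has true variance (s2 + S·t2)/S. The random-intercept model treats it as (s2 + S·t2/(T−1))/S. The true-to-reported SE ratio is therefore r = √[(s2 + S·t2)/(s2 + S·t2/(T−1))], and type I error is 2(1 − Φ(1.96/r)).

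Example, T = 5, residual SD 0.5, slope SD 0.3: r = √(1.15/0.475) = 1.556, giving 20.8%.

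| Slope SD | T=5, residual SD 0.5 | T=5, residual SD 1 | T=3, residual SD 0.5 | T=3, residual SD 1 |
|---|---|---|---|---|
| 0 | 5.0% | 5.0% | 5.0% | 5.0% |
| 0.1 | 8.2% | 5.8% | 5.4% | 5.1% |
| 0.2 | 15.0% | 8.2% | 6.6% | 5.4% |
| 0.3 | 20.8% | 11.6% | 8.1% | 6.0% |

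Simulation (2,000 datasets per setting, five visits, slope SD 0/0.1/0.2/0.3) agrees: 5.4/8.9/14.1/21.3% at residual SD 0.5 and 4.9/6.8/8.2/11.2% at residual SD 1. Because enrolment is spread out ("Our goal is to enroll 150 patients of all ages and from all CDG types over 5 years in the natural history study"), follow-up of one to five visits, equally likely, was also run: 4.5/7.7/14.2/21.2% and 5.2/6.3/8.1/11.4%. With a five-category score analysed as numeric (five visits, slope SD 0/0.2/0.3), the rates were 4.7/13.3/16.9% and 4.5/8.3/10.7%.

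With concurrent Quality of Life as predictor the effect is milder. With five visits the rates were 4.9/4.2/8.9/14.1% at residual SD 0.5 and 5.4/4.5/5.2/6.6% at residual SD 1.

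**Reading (b): successive PRO change as response.** A difference has variance 2·s2 + t2, and adjacent differences have covariance t2 − s2. With t2 = 0 their correlation is −0.5. A random intercept cannot represent a negative correlation, so its variance estimate goes to about zero. Five visits give four differences and three adjacent pairs. The true-to-reported variance ratio is then 1 + 2·(3/4)·(−0.5)·ρ, where ρ is the adjacent correlation of the predictor.

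- Quality of Life change: ρ = −0.5, ratio 1.375, SE ratio 1.173, type I error 9.5%.
- Quality of Life level: ρ = 1/(1 + s2) = 0.8 or 0.5, ratio 0.40 or 0.625, SE ratio 0.632 or 0.791, type I error 0.2% or 1.3%.

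These figures have no slope variation, so the omitted slope is not the cause. Simulations over the slope SDs above gave about 6 to 10% on change and 0 to 4% on level.

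**Reading (c): Quality of Life as response, PRO change as predictor.** With five visits, simulated rates were 3.7 to 5.9% for successive change. For change from baseline they were 4.2 to 7.7%, except 9.9 to 10.7% at slope SD 0.3 with residual SD 0.5.

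**With the remedy.** Participant-clustered robust standard errors on the random-intercept model gave 3.8 to 7.6% across the settings run under (a) and (b). For baseline Quality of Life by time, adding a random slope gave 3.9 to 6.2% model-based and 3.8 to 8.1% robust.

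**The case against.** The strongest reply is that the sentence is about change, so the missing slope may be beside the point. That stands in part. Under (b) the slope is not the cause, and under (c) the stated model is mostly near nominal.

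Next, the largest rates belong to baseline Quality of Life by time. The plan's time-constant-factor rule may be meant to cover that case, and then the problem does not arise. That also stands, but the PRO sentence states a different structure, and the two need reconciling.

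Third, every size rests on assumed SDs. Slope SD 0.3 with intercept SD 1 and residual SD 0.5 is a strong assumption: PRO variance would rise from 1 + 0.25 = 1.25 at baseline to 1.25 + 16 × 0.09 = 2.69 four years later. At slope SD 0.1 with residual SD 1, the excess is under one percentage point. No logit or ordinal link was simulated, although the plan speaks of generalized linear models.

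A reader might infer that this test will produce false positives at two to four times the nominal rate. The documents do not support that. They fix neither the response nor any slope variance. The Background statement that "clinical CDG manifestations are widely variable within and among subtypes and across the lifespan" concerns clinical features; it makes varying PRO slopes plausible but does not show them.

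Finally, the test has no stated significance level, power or decision rule, and the plan relies on the coordinating center's statisticians. That lowers the importance. It does not make the written model adequate under (a) with varying slopes, or under (b).

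**Conclusion.** The concern holds conditionally and is of modest importance. As written, the test can have wrong model-based standard errors under both readings in which the PRO is the response. Under (a) it is too liberal if slopes vary: with five visits, about 6 to 8% at slope SD 0.1 and 12 to 21% at 0.3 for baseline Quality of Life by time. For concurrent Quality of Life the range is about 4 to 9%, rising to about 14% at the extreme. There is no inflation if slopes do not vary, and little with three visits (at most 8.1%). Under (b) the test is too liberal on Quality of Life change and too conservative on Quality of Life level. Under (c) it is close to nominal except at the extreme setting. The documents establish the unstated response and the differing random-effects structures. The sizes rest on the assumed SDs, the 5% level and a numeric score.

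**What to change.** Amend the PRO validation paragraph as follows.

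- State the response, and how change is coded.
- Under any reading, report participant-clustered robust standard errors with a named small-sample correction, for example a bias-reduced sandwich with a t reference. The simulated robust rates of up to 7 to 8% already used a simple m/(m − p) factor (m participants, p coefficients), so a better correction is worth naming. The bias-reduced version was not itself simulated.
- If the response is the repeated PRO score, also add a random slope for time or age, as in the age-trend and time-constant-factor models. Fall back to a random intercept with robust standard errors if the slope variance cannot be estimated, as may happen with few visits.
- For clarity, name the Quality of Life questions.

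This changes SAP wording only and needs no new data. The cost is wider intervals where the present ones are too narrow. For baseline Quality of Life by time, a random slope widens them by about 2% if slopes do not vary. With five visits and slope SD 0.1/0.2/0.3, it widens them by 13/36/56% at residual SD 0.5 or 4/13/24% at residual SD 1. Under (b), robust intervals are 5 to 18% wider on Quality of Life change and 9 to 36% narrower on Quality of Life level.

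### Weighted kappa is the only reliability statistic named for repeat PRO scores. For summary scores an ICC from a mixed model on all stable visits, with patient-level intervals, would be better.

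*Combined protocol and SAP*

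**What the plan says.** Aim 2 (Research Question and Aims) is to validate the CDG rating scale and the PRO and quality-of-life measures. Under Study Activities, the PROMIS questionnaire is one of the surveys completed at each visit, and visits are annual. That section does not say whether items, totals or scaled scores are analysed.

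The last paragraph of the Data Analysis Plan uses the PROs in three ways:

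- Validity: "Partial least squares (PLS) regression analysis will be utilized to identify patterns of association between the PROs and the clinical scores".
- Change: "Changes in PRO scores over time will be tested for association with Quality of Life questions using random effects generalized linear regression models", with the models "incorporating a random intercept for each participant".
- Reliability: "We will also compare subsequent scores on the PROs from the same subject to determine reliability of the PRO", provided clinical status has not changed significantly. The statistic follows: "Reliability will be assessed by the weighted Kappa to account for the ordinal variables".

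Nothing more is said about reliability. The plan gives no weighting scheme, categories, number of pairs per patient or interval method.

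The number of PRO scores per patient is not stated directly. The optional research samples are taken "once per year over the course of 5 years of follow up", and the Biospecimens section allows up to five annual blood draws. Because surveys are done at each visit, up to about five PRO scores per patient is a fair inference, but only an inference.

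**The concern.** The point is the choice of statistic, not the time between scores. There are two issues.

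1. **Coefficient.** Weighted kappa is defined on categories with a weight for each degree of disagreement. An ordinal item supplies its own categories, so only the weights are open. A summed or scaled score must first be cut into bins, and then bins and weights are both open. Neither is fixed in advance, so the same data can give materially different reliability figures, and the choice could be made after the data are seen.

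2. **Number of occasions.** Kappa compares two occasions. A patient with three or more stable visits gives several pairs that share scores. The analyst must then discard visits or pool dependent pairs. Pooling with the usual large-sample standard error treats every pair as a separate patient. The plan accounts for within-patient correlation in its trend and change models but is silent on it for reliability.

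What is at stake is how the reliability part of Aim 2 can be read: a coefficient that cannot be interpreted without its weights and bins, and possibly an interval that is too narrow.

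**Working it through.** **No figure to reproduce.** The plan gives no kappa, standard error, interval or power for reliability, and the Accrual section bases sample size on a patient count and census. The calculations below are simulations under stated assumptions.

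**From the documents:** target accrual of 150; annual visits with PROs at each; up to about five visits (inferred).

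**Assumed:** normally distributed scores with a random patient intercept and exchangeable visits; ICC 0.80 unless stated; 3 to 10 equal-frequency categories for the coefficient and five for the standard errors.

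**Formulas**

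- Weighted kappa = (Po − Pe)/(1 − Pe), where Po and Pe are the weighted observed and chance agreement.
- With K categories, the weight for cell (i, j) is 1 − |i − j|/(K − 1) (linear) or 1 − (i − j)²/(K − 1)² (quadratic).
- ICC = patient variance / total variance.
- Pairs per patient with V visits: V − 1 consecutive, or V(V − 1)/2 in all. Five visits give 4 or 10; three give 2 or 3; two give 1.

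**Step 1: weights and bins** (1,000,000 simulated pairs)

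| True ICC | Linear, 3 to 10 categories | Quadratic, 3 categories | Quadratic, 5 | Quadratic, 10 |
|---|---|---|---|---|
| 0.80 | 0.57 to 0.58 | 0.69 | 0.75 | 0.78 |
| 0.90 | 0.70 to 0.71 | 0.80 | 0.85 | 0.88 |

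At ICC 0.80 the gap between quadratic and linear weights with 10 categories is 0.78 − 0.57 = 0.21. Allowing skewed categories and up to 20 of them, kappa runs from 0.55 to 0.78 at ICC 0.80 and from 0.45 to 0.68 at ICC 0.70. The weights matter most. Bins matter mainly with quadratic weights and few categories.

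**Step 2: pooled pairs.** The ratio is the empirical SD of kappa divided by its mean large-sample standard error. Results for 100 stable patients, ICC 0.80, five categories, over both weightings:

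| Visits per patient | Pairs pooled | Ratio | Coverage of nominal 95% interval |
|---|---|---|---|
| 5 | all (100 × 10 = 1,000) | 2.1 to 2.3 | about 63% |
| 5 | consecutive (100 × 4 = 400) | about 1.5 | about 80% |
| 3 | all (300) or consecutive (200) | 1.4 to 1.5, or 1.2 | 83% to 89% |
| 2 | one pair each (100) | about 1.0 | close to nominal |

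The target of 150 patients with quadratic weights gives the same picture: 0.0287/0.0191 = 1.50 for 600 consecutive pairs, 0.0263/0.0120 = 2.19 for all 1,500 pairs, and 0.0375/0.0378 = 0.99 for one pair per patient.

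**Step 3: what an ICC would give.** With n patients and k visits, the large-sample SE is (1 − r)(1 + (k − 1)r)√(2/(k(k − 1)(n − 1))); this simple form has no separate visit variance. For n = 150, k = 5, r = 0.80: 0.20 × 4.2 × √(2/2,980) = 0.0218. With k = 2 it is 0.0295. Using all five visits therefore shortens the interval by about a quarter (1 − 0.0218/0.0295 = 0.26), with the patient as the unit. ICC and kappa are different coefficients, so setting 0.0218 beside the naive kappa error of 0.0120 only indicates scale.

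**The case against.** The plan says kappa is chosen because the variables are ordinal, and weighted kappa is a standard choice for ordinal items. The documents do not say that totals will be binned; if single items are analysed, the bin problem disappears. This stands, and it limits the point to summary or scale scores. The weights and the handling of repeated pairs stay open even for items.

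A reader might infer that the plan contradicts itself by treating PROs as numeric in some places and categorical in another. The documents do not support that. Generalized models can take ordinal responses, ordinal scores can be entered in PLS, and "Changes in PRO scores over time will be tested for association" does not commit the plan to subtracting scores. These uses make an analysis of scores likely; they do not prove an inconsistency.

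A reader might also infer that the plan reports an interval that is too narrow. It promises no interval and does not say pairs will be pooled, so that defect is conditional. Five usable scores per patient is an upper limit: the explicit five-year and five-visit wording concerns samples, enrolment itself runs over 5 years, and only clinically unchanged periods count.

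Finally, linear kappa is a different quantity from the ICC, so a lower value is not an error, and quadratic kappa with 10 categories (0.78) is close to an ICC of 0.80. This is right. Fixing quadratic weights would settle much of the coefficient, but it would still bin the scores and compare only two occasions at a time.

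**Conclusion.** The point holds as a cheap improvement, not as an error in a stated analysis. For summary or scale PRO scores, an unspecified weighted kappa can differ by about 0.2 for the same data (0.57 to 0.78 at an assumed ICC of 0.80). It also does not readily use more than two visits. If pairs were pooled with the usual standard error, that error would be too small by a factor of about 1.2 to 1.5 with three visits and 1.5 to 2.3 with five. The five-visit figure is an upper-end case (100 stable patients, ICC 0.80, five categories). With one pair per patient there is no understatement of any consequence. ICC values, category counts and exchangeable visits are assumptions; the directions held at every ICC tried from 0.5 to 0.9.

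Two larger claims about stakes are tempting but unsupported. The documents do not say that reliability is half of the PRO evidence: Aim 2 also covers the rating scale, and the plan lists clinical comparisons, PLS and change analyses as well. Nor do they say that the coefficient will be used to size later trials or be judged against a threshold.

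**What to change.** Replace the reliability sentence in the Data Analysis Plan with two:

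1. For PRO summary or scale scores, reliability is an absolute-agreement ICC from a mixed model on all clinically stable visits: patient variance / (patient + visit + residual variance). The confidence interval comes from a patient-level bootstrap or profile likelihood. The standard error of measurement, √(visit + residual variance), is reported with it.
2. For single ordinal items only, reliability is a weighted kappa with quadratic weights fixed in advance, using either one pair per patient or a patient-level bootstrap interval.

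The data are unchanged, no assessment is added, and mixed models are already in the plan. The cost is slightly more analysis work and intervals wider than a naive pooled kappa would show.
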